#### **3.6.3** Other Safety Evaluations

#### 3.6.3.1 Vital Signs

The observed values, along with the changes from baseline, will be summarized by visit and by treatment for systolic and diastolic blood pressure (mmHg), pulse rate (beats/min), respiratory rate (breaths/min), body temperature (°C), and body weight (kg). Shift analysis of following BMI categories will be performed:

- Underweight (<18.5 kg/m^2)
- Normal weight ( $\geq 18.5 \text{ kg/m}^2 \langle 25 \text{ kg/m}^2 \rangle$ )
- Overweight ( $\geq 25 \text{ kg/m}^2 <30 \text{ kg/m}^2$ )
- Obese ( $\geq 30 \text{ kg/m}^2$ ).

For vital sign assessments collected on the dosing day, the vital sign data will be presented by time points of interest as well. The time points of interest are as follows:

- Pre-dose assessment.
- During dosing: 15 minutes, 45 minutes, 75 minutes after start of infusion.
- After dosing: immediately after infusion, 60 minutes post-infusion.

In addition, a summary of subjects with clinically significant vital signs values (meeting any of following criteria) will also be provided:

- Systolic blood pressure: < 90 mmHg, > 140 mmHg, > 160 mmHg
- Diastolic blood pressure: < 50 mmHg, > 90 mmHg, > 100 mmHg
- Pulse rate: < 60 beats/min, > 100 beats/min
- Respiratory rate: < 12 breaths/min, > 20 breaths/min
- Body temperature: < 36°C, >38°C
- Body weight: decrease of  $\geq$  7% from baseline and increase of  $\geq$  7% from baseline.

#### 3.6.3.2 Electrocardiogram

The observed values, along with the changes from baseline, will be summarized for ventricular heart rate (bpm), PR interval (msec), QRS duration (msec), QT interval (msec), and the corrected QT interval (QTc) based on Bazette approach and based on Fridericia approach. The number (%) of subjects meeting the following criteria will be summarized:

- QTc > 450 msec
- QTc > 480 msec

- QTc > 500 msec
- QTc increases from baseline > 30 msec
- QTc increases from baseline > 60 msec

In addition, the overall clinical evaluation of electrocardiogram results (normal, abnormal, not clinically significant abnormal, potentially clinically significant abnormal) will be summarized.

#### 3.6.3.3 Physical Examination

The findings from physical examinations will be recorded. Those clinically significant abnormal findings that meet criteria for an AE will be reported as such. All abnormal physical exam findings (including not clinically significant and potentially clinically significant) will be listed.

#### 3.8 Immunogenicity

The ADA analysis will be based on the Safety Analysis Set. The ADA status in Table 9Error! Reference source not found. will be summarized by the categories included in the table and the ADA titer may be summarized for ADA positive subjects. The impact of ADA on safety may be evaluated if needed.

ADA Status	Definition
Prevalence (Positive during the study)	ADA positive observed at least once during the study (baseline included)
Incidence (treatment emergent ADA)	ADA positive post-baseline only or boosted their pre-existing
	ADA titer ( $\geq$ 4-fold increase) during the study period
Negative during the study	ADA positive not observed at any visit during the study (baseline included)
Baseline positive	ADA positive observed at baseline regardless of the post- baseline ADA status
Post-baseline positive	ADA positive observed at least once during post-baseline regardless of the baseline ADA status
Only baseline positive	ADA positive observed at baseline but not observed at any time post-baseline
Only post-baseline positive (treatment-induced)	ADA positive not observed at baseline but observed at least once post-baseline
Both baseline and post-baseline positive	ADA positive observed at baseline and observed at least once post-baseline

Table 9 Definition	of ADA Status
---------------------------	---------------

Persistent positive	Treatment-induced ADA positive at $\geq 2$ post-baseline assessments (with $\geq 16$ weeks between first and last positive) or positive at last post-baseline assessment
Transient positive	Treatment-induced ADA post-baseline positive but does not fulfil the criteria of persistent positive

ADA = anti-drug antibodies.

#### **4 PLANNED ANALYSIS**

Two analyses are planned for this study. The primary analysis will be conducted after the last subject enrolled in the study has completed the RCP or discontinued prematurely. All the data collected by the date of the last visit during the RCP (or within 5 business days after the scheduled visit window for the last visit in case any data may be collected after the last scheduled visit, for example, image data etc.) will be included in the primary analysis. The final analysis will be performed after all subjects have completed the study or discontinued prematurely.

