1 SYNOPSIS

Title	A Phase 3, Randomized, Double-blind, Multicenter, Placebo-Controlled Study of Inebilizumab Efficacy and Safety in IgG4 Related Disease
Short Title	MITIGATE
Phase	3
Study Design	Randomized, double-blind, placebo-controlled, parallel-cohort study
Rationale	There are currently no medicinal products approved for the treatment of immunoglobulin G4-related disease (IgG4-RD), a rare disease. The majority of cases follow a relapsing course that can lead to permanent tissue damage with attendant morbidity and potential mortality. Glucocorticoids (GCs) are widely and effectively used for acute treatment of initial disease activity and of recurrent episodes (flares), but GCs do not prevent recurrence of active disease during their taper or after their discontinuation. Moreover, GCs are associated with substantial toxicity. Thus, there is a high unmet medical need for therapies that prevent disease recurrence and limit GC exposure. The pathogenesis of IgG4-RD suggests that B-cell depletion may be an effective avenue for therapeutic intervention. An important role for B cells, particularly plasmablasts and plasma cells, in the pathogenesis of the disease appears likely. The anti-CD19 B cell-depleting activity of inebilizumab suggests that it may provide benefit as treatment for IgG4-RD. This study aims to define the efficacy and safety of inebilizumab for the prevention of flare of IgG4-RD.
Target Population	Male or female adults, who have reached the age of consent in the applicable region, who have recently active IgG4-RD (initial diagnosis or flare) that requires new or ongoing treatment, are at high risk of future flare (as evidenced by multi-organ disease involvement), and meet the 2019 American College of Rheumatology/European League Against Rheumatism (ACR/EULAR) IgG4-RD classification criteria.
Number of Subjects	Approximately 160 subjects will be randomized and dosed in a 1:1 ratio to 2 treatment groups; approximately 80 subjects to each treatment group. Enrollment may be increased to a maximum of 200 subjects total based on blinded event-rate analysis.
Length of Participation	Screening period: Up to 28 days Randomized-control period (RCP): 365 (± 7) days Optional open-label period (OLP): 1,095 (+ 10) days Safety Follow-Up period (SFUP) after investigational product (IP) discontinuation: 730 days Total maximum duration of study participation: 2,273 days

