6.3.2.2 IgG4-RD Responder Index

The IgG4-RD RI is a validated instrument for longitudinal assessment of IgG4-RD disease activity, developed and refined by an international team of IgG4-RD experts specifically to permit structured assessment of response to treatment by clinical investigators (Carruthers et al, 2012; Wallace et al, 2018). The RI captures disease activity and damage in 25 domains, with higher weights for disease manifestations that require urgent treatment or that worsen despite treatment. The RI incorporates an activity score for each organ/site of disease, a score for symptomatic disease at each of these sites, and a score amendment for a need for urgent treatment. Serum IgG4 concentration and presence of organ-specific damage are collected but are not part of the overall RI. Because visit-to-visit consistency is important, whenever possible, the same Investigator should complete the IgG4-RD RI for the same subject across all visits.

Not all results needed to complete the IgG4-RD RI (in particular, labs and imaging) will be available at the time of the subject's visit. Therefore, the investigator may delay completion of the IgG4-RD RI for up to 15 business days of the visit date to permit all results to be considered. All other assessments related to the IgG4-RD RI should be completed on the day of the visit.

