7.4.4 Extent and Maintenance of Blinding

This is a double-blind study in which inebilizumab and placebo are matched in appearance.

The Sponsor will remain blinded until after the database lock for primary efficacy analysis, which will occur after all subjects have completed the Day 365 visit (Visit 15) or discontinued early from the RCP. Subjects, site staff, and contract research organization (CRO) personnel will remain blinded to individual subject treatment assignment until final database lock at the conclusion of the study. Potentially unblinding laboratory data will not be available to investigative site personnel until after final database lock.

If treatment allocation for a subject becomes known to the Investigator or other study staff involved in the management of study subjects, the Sponsor must be notified immediately.

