different sample sizes between 160 and 200 in increments of 10. For each of the sample sizes, this simulation process will be repeated 10,000 times to give a distribution of the number of flares. The target sample size is the one that achieves 39 flares 90% of the time.

If the blinded assessment from these first 50 dosed subjects indicates that the number of flares expected with 160 subjects is less than 39, then the sample size may be adjusted based on the above exercise to the number of subjects anticipated to achieve 39 flares with a maximum of 200 subjects (100 subjects per treatment group).

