9.5 Methods for Statistical Analyses

9.5.1 Analysis of the Primary Efficacy Endpoint

The primary efficacy analysis will use the treatment policy strategy, which includes all data captured during the 52-week RCP.

The primary efficacy variable is the time in days from Day 1 (dosing) to the date of the first treated and AC-determined IgG4-RD flare within the 52-week RCP. The date of disease flare is defined as the date of initiation of any flare treatment (new or increased GC treatment, other immunotherapy, or interventional procedure) deemed necessary by the Investigator for the flare. The hazard rate in the inebilizumab group will be compared to that in the placebo group using the Cox proportional hazards model with the treatment indicator (inebilizumab or placebo) and the stratification factor as the explanatory variables. The HR of inebilizumab versus placebo will be estimated together with its associated 95% CI. SAS PROC PHREG will be used for fitting this model. The data cutoff for the primary analysis will be when all subjects have completed or discontinued from the RCP.

Subjects who discontinue prematurely from the RCP without a treated and AC-determined flare will be censored in this model at the time of discontinuation.

Additional analysis with the same model will be performed with data from subjects who meet the following criteria, censored at the time the relevant treatment was first received:

- Received any treatment for IgG4-RD, including GC or immunosuppressive treatment, prior to experiencing a treated and AC-determined flare; or
- Received any prohibited GC or immunosuppressive treatment prior to experiencing a treated and AC-determined flare.

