#### 3.1.2 Analysis Windows

Analysis visit windows will be used for all visit-based assessments to map longitudinal observations to scheduled visits and, thereby, allow for by-visit analyses, since not all assessments are performed on the scheduled day. Unless otherwise specified, all longitudinal efficacy and safety data analyses will be based on the analysis visit windows except the IgG4 RI. The analysis visit windows will be calculated by bisecting the interval between adjacent scheduled visit days, or by  $\pm$  14, 30, or 60 days from the scheduled RCP, OLP, or SFP visit dates, respectively, whichever results in a shorter interval. The IgG4 RI will need the data from lab or image results, which may not be available until several weeks after the scheduled visit. Hence, the IgG4 RI will be summarized by the nominal visit per protocol.

The actual assessment day will be mapped to the windows defined for each scheduled study visit with following rules:

- If more than one assessment falls within a visit window, the closest non-missing assessment to the scheduled day will be used in the analysis.
- If two non-missing assessment actual dates are equidistant from the target day, the later visit will be used in the analysis.
- For retest values of laboratory data, the retest value (the last valid observation assessed on the same visit day) will be chosen.

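### Does the SAP's 5-business-day data cut exclude Week 52 Responder Index scores that the protocol allows 15 business days to complete?

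*SAP*

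**What the plan says.** SAP section 4 places the primary analysis after the last enrolled subject completes or leaves the randomized-controlled period (RCP). It includes data collected by the last RCP visit, or "within 5 business days after the scheduled visit window for the last visit", and names imaging as an example of what may come late.

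Protocol section 6.3.2.2 recognises that laboratory and imaging results may be outstanding at the visit, so "the investigator may delay completion of the IgG4-RD RI for up to 15 business days of the visit date". It then adds: "All other assessments related to the IgG4-RD RI should be completed on the day of the visit".

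The Week 52 window is set in the Protocol synopsis: "Randomized-control period (RCP): 365 (± 7) days". SAP 3.1.2 has a separate set of analysis windows ("14, 30, or 60 days from the scheduled RCP, OLP, or SFP visit dates") but exempts the RI from them. It notes that RI inputs can take several weeks and assigns the score to its nominal visit.

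SAP 3.5.2.2 and 3.5.2.3 score a subject with no Week 52 disease-activity assessment as not in remission. Both accept either an RI of 0 or an investigator's determination that no disease activity is present. One additional analysis in SAP 3.5.2.2 accepts only an RI of 0.

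Protocol 9.5.1 states: "The data cutoff for the primary analysis will be when all subjects have completed or discontinued from the RCP". Protocol 7.4.4 describes the lock for the primary efficacy analysis as one "which will occur after all subjects have completed the Day 365 visit (Visit 15) or discontinued early from the RCP".

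**The concern.** Two clocks apply to the same assessment: 5 business days from the close of the visit window, and 15 business days from the visit. SAP 4 does not mention the RI and does not define what counts as collected. SAP 3.1.2 settles which visit a late RI belongs to, not whether it enters the primary analysis.

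If the cut applied to completion of the score, an investigator could meet the protocol deadline and still have the Week 52 RI left out. A subject in true remission could then be counted as a failure. Two of the three key secondary endpoints under type I error control use that assessment, and the sponsor is unblinded after this lock, so a rule settled late would be open to question.

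**Working it through.** **1. The two deadlines.** Inputs: window end Day 365 + 7 = Day 372 (Protocol synopsis and Table 4); cut = window end + 5 business days (SAP 4); RI deadline = visit + 15 business days (Protocol 6.3.2.2). With weekday visits and no public holidays (an assumption), 5 business days are 7 calendar days and 15 are 21.

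Cut: 372 + 7 = Day 379.

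| Week 52 visit | RI deadline (visit + 21) | Beyond the cut |
|---|---|---|
| Day 358 | Day 379 | 0 |
| Day 365 | Day 386 | 7 calendar = 5 business days |
| Day 372 | Day 393 | 14 calendar = 10 business days |

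If the 14-day analysis window of SAP 3.1.2 were meant, the cut would be 379 + 7 = Day 386 and the gaps 0, 0 and 5 business days. Under the ±7-day window, the last subject has no gap if the RI is finished within 10 business days of a Day 365 visit, or within 5 of a Day 372 visit.

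**2. Who could be affected.** Both SAP 4 and Protocol 9.5.1 tie the primary analysis to the last subject, so the natural cut is study-level. Everyone who finished well before the last subject has passed the 15-day deadline by then. Only subjects enrolled within d days of the last one are exposed, with d = 7 if all visits fall on Day 365 and d = 14 if all fall on Day 372. Assume uniform accrual over 12 to 36 months (the documents give no rate), N = 160, no dropout and every subject using all 15 business days. The expected count is 1 + N × d / (7 × weeks of accrual):

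- Day 365 visits: 1 + 160 × 7/364 = 4.08 at 12 months; 1 + 160 × 7/1092 = 2.03 at 36 months.
- Day 372 visits: 1 + 160 × 14/364 = 7.15 at 12 months; 1 + 160 × 14/1092 = 3.05 at 36 months.

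Full use of the allowance by everyone drives these counts. If completion were instead uniform over 0 to 15 business days (also an assumption), the last subject is late with probability 7/21 or 14/21, and the other exposed subjects with half that on average:

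- Day 365 visits: 1/3 + (160 × 7/364)/6 = 0.85 at 12 months; 1/3 + (160 × 7/1092)/6 = 0.50 at 36 months.
- Day 372 visits: 2/3 + (160 × 14/364)/3 = 2.72 at 12 months; 2/3 + (160 × 14/1092)/3 = 1.35 at 36 months.

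These count scores that might be completed after the cut. They are not counts of lost remitters and should not be read as an effect size.

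**3. What a loss would require.** A subject is misclassified in a key secondary endpoint only if all of these hold: SAP 4 is read as excluding late-scored indices; the subject is among the last few; the RI is completed after the cut; the subject is otherwise a remitter; and no investigator determination of no disease activity is recorded by the cut. Each such loss moves one arm by 1/80 = 1.25 points, or 1/100 = 1.0 point at the maximum sample size of 200.

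**4. Which reading fits the text.** SAP 4 states what will be included, by date of collection, and nowhere says that a later score is dropped. Protocol 6.3.2.2 requires the other RI assessments on the visit day, and Table 4 schedules Week 52 sampling at that visit, so the usual inputs are already collected. Protocol 9.5.2.3 bases the remission analyses on everything captured in the RCP, and the RI is a scheduled Week 52 procedure. SAP 3.1.2 was written for RI inputs that arrive weeks late. Discarding those scores would defeat that provision.

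**The case for a change.** The strongest reply is that none of this is explicit. SAP 4 puts imaging under the 5-day allowance, and imaging is one of the inputs that Protocol 6.3.2.2 says delays the RI. The investigator's determination can rest on laboratory or pathology evidence, so it may wait on the same late results. The additional analysis in SAP 3.5.2.2 has no second route. One sentence would close the matter before unblinding.

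Part of this stands. The two allowances are not expressly reconciled, and that additional analysis would lose any RI left out, though it lies outside the multiplicity procedure.

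The rest is weaker than it looks. The readable part of Table 4 shows no Week 52 imaging (some rows are redacted), and Protocol 6.3.6 leaves imaging beyond the baseline and pre-randomization scans to the investigator's discretion. The summary of changes for Amendment 9 gives the reason for the investigator route: subjects without active disease should not fail for want of imaging. Nor is it shown that scores would be kept or dropped ad hoc. Protocol 7.4.4 sets no 5-day limit on lock, and Protocol 11.5.1 leaves data-handling procedures to a Data Management Plan that is not part of these documents. Nothing forces a lock before outstanding scores are entered.

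**Conclusion.** The mismatch of 5 and 15 business days is real on paper, but it is a missing detail that the study team can fill sensibly from the plan's own text: a Week 52 RI completed within the protocol's 15 business days, from findings and samples taken at the visit, belongs in the primary analysis.

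On the restrictive reading, the shortfall is 0 to 10 business days for the last few subjects only. Any exclusion would follow calendar date under blinding, so it gives no reason to expect type I error inflation. The primary time-to-flare endpoint is untouched, and both key secondary remission endpoints keep the investigator route. A lost remitter would cost 1.25 points in one arm (1.0 at N = 200), with no stated probability of that happening.

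This conclusion rests on the study-level reading of the cut. If the cut ran from each subject's own Week 52 window, most subjects could be exposed, but the wording of SAP 4 and Protocol 9.5.1 points the other way. Stating in SAP 4 that the cut is study-level and that on-time Week 52 scores and determinations count would be harmless and optional. The results and conclusions would be sound without it.

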#### 5 MULTIPLICITY ADJUSTMENT

The primary null hypothesis will be tested at two-sided  $\alpha = 0.05$ . If, and only if, the treatment group comparison is statistically significant, the secondary hypotheses will be tested.

The 3 key secondary endpoints to be considered for study-wise type I error control are:

- 1. Annualized flare rate for treated, AC-determined flares during the RCP.
- 2. The proportion of subjects achieving flare-free, treatment-free complete remission at Week 52.
- 3. The proportion of subjects achieving flare-free, corticosteroid-free complete remission at Week 52.

Null hypotheses for the key secondary endpoint #1 and #2 will be tested in parallel with  $\alpha = 0.025$ . The key secondary endpoint #2 and #3 will be tested sequentially: if the null hypotheses is rejected for the key secondary endpoint #2, the null hypothesis for the key secondary endpoint #3 will be tested with  $\alpha = 0.025$ . If the null hypothesis for the key secondary endpoint #1 is rejected, the alpha will be recycled to test the key secondary endpoint #2 and #3 are rejected, the alpha will be recycled to test the null hypotheses for the key secondary endpoint #2 and #3 are rejected, the alpha will be recycled to test the null hypotheses for the key secondary endpoint #2 and #3 are rejected, the alpha will be recycled to test the null hypotheses for the key secondary endpoint #2 and #3 are rejected, the alpha will be recycled to test the null hypothesis for the key secondary endpoint #1. (See Figure 2)

